6.1.3 Treatment Periods

Assessments of a single visit can be split over up to 2 consecutive days, if required. If more than 2 days are needed, approval is required from the medical monitor in advance.

6.1.3.1 Baseline Visit

If needed, all assessments that need to be performed pre-dose can be done over 2 consecutive days (i.e. Day 0 or Day 1); any exceptions to doing over 2 consecutive days due to an open biopsy with general anesthetic must be discussed with the medical monitor in advance for approval. There must be at least 24 hours between the biopsy and IMP administration. The investigator is

to get approval from the medical monitor if additional time is required to perform all needed Pre-dose/Baseline assessments.

6.1.3.2 Single Ascending Dose Part

Subjects will receive a single IV administration of DYN101 on Day 1, after which they are followed for 4 weeks up to Day 29.

There will be a subsequent washout period of at least 12 weeks: during Weeks 5-17, subjects will be asked to visit the site every 2 weeks for safety follow-up, even if they do not continue to the MAD part. Where possible, the visits will take place on the same day of the week as the visit on Day 1.

Due to restrictions imposed in response to a pandemic that restrict subject visits, please contact the medical monitor to determine the strategy for continuing the subject in the trial. All efforts must be employed to maintain subject safety. Assessments, if feasible, must be collected during a phone call with the subject. The site should arrange the collection of the blood and urine samples, if at all possible.

Every 2 weeks following the Week 17 visit, subjects will be contacted by phone by qualified site personnel to follow-up on concomitant medications and AEs, until their assigned MAD cohort has been opened.

Subjects who participated in the SAD part will subsequently participate in the MAD part (provided the IDMC has given a favorable advice to proceed, see Section 3.1.1).

6.1.3.3 Multiple Ascending Dose Part

For subjects for whom the last visit in the SAD part was more than 3 months before the baseline visit in the MAD part, there will be an unscheduled visit (physical examination and clinical laboratory parameters) which will occur between 6 weeks and 7 days prior to the MAD baseline visit. Liver ultrasound and hepatic elastography have to be performed before the baseline visit in the MAD part. The first IMP administration in the MAD part cannot be started before the liver ultrasound and hepatic elastography results are available.

Subjects will receive weekly IV administrations of DYN101 for a period of 12 weeks, i.e. from MAD Week 1 to Week 12.

Replacement of withdrawn subjects can occur under the circumstances described in Section 3.1.2. New subjects who did not participate in the SAD part should sign an ICF for participation in the MAD part, and the eligibility will be assessed (see Section 6.1.1) before the first IMP administration in the MAD part (MAD Week 1 Day 1). Replacement subjects may or may not need a run-in period, in consultation with the sponsor (see Section 6.1.2). A DNA sample (optional) and a muscle biopsy should be taken before the first IMP administration.

6.1.3.4 MAD Extension Part

After completion of the MAD part, subjects will continue on the IMP dose level of their assigned MAD cohort for an additional 12 weeks with weekly IV administrations (MAD Weeks 13-24) (unless the IDMC advises otherwise).

End-of-treatment assessments will be performed after 24 weeks of MAD treatment have been completed, i.e. at the Week 25 visit.

After Week 24, all subjects will remain on treatment with weekly IMP administrations and assessments every 2 weeks until the last MAD3 subject has completed the MAD Week 25 visit. Data collected during this period will be listed and tabulated in the clinical trial report but will not be included in the statistical modeling.

6.1.4 End of Treatment Follow-up Visit

If a subject is NOT continuing on IMP treatment after the trial, the subject will return to the clinic for an EoT follow-up visit 3 months after the last IMP administration, to follow-up on the subject's status including abnormal laboratory results, AEs, and concomitant medications. The follow-up information will be recorded in the eCRF.

6.1.5 Early Discontinuation

In case subjects are withdrawn from IMP or from the trial, there will be a follow-up visit to query for AEs/SAEs and concomitant medications. In addition, safety, PK and PD/exploratory efficacy assessments may be performed at this early discontinuation visit. The assessments to be performed at this visit correspond to the assessments of the MAD Week 25 visit (excluding IMP administration) (refer to the [TRIAL SCHEDULES](#)). In addition, subjects participating in MAD are encouraged to have a second muscle biopsy taken if the subject had at least 6 weeks of treatment during the MAD part of the trial and discontinued prior to having the Week 13 biopsy obtained; SAD subjects do not need a second muscle biopsy.

If subjects agree, they will also have an EoT follow-up visit 3 months after their last IMP administration.

6.1.6 Additional Care of Subjects After the Trial

The sponsor will consider providing IMP to subjects after the last visit in this trial, including stand-by subjects.

6.2 Trial Evaluations

Further details will be described in the site manuals (e.g. Laboratory Manual, Site Operations Manual, Pharmacy Manual).

6.2.1 Demographic and Other Baseline Characteristics

Demographic data such as age, gender, race and ethnicity, and other baseline characteristics including medical history will be recorded.

6.2.2 Safety Evaluations

The investigators, together with the medical monitor, will be responsible for the safety monitoring of the trial, and will pause IMP administration of further subjects in case any of the pre-specified pausing/stopping rules described in Section [7.11.1](#) occur.

An IDMC will be appointed by the sponsor before the start of the trial to perform regular reviews of the emerging safety data during the trial. Details regarding the IDMC are provided in Section [9.12](#).

Abnormal results for any safety evaluations, which are unexpected or not explained by the subject's clinical condition may be, at the discretion of the investigator or sponsor, repeated until confirmed, explained, or resolved as soon as possible.

6.2.2.1 Adverse Events

At each trial visit, subjects will be questioned in a general way to ascertain if AEs have occurred since the previous visit (e.g. "Have you had any health problems since your last visit?"). AEs are collected from signing of the main ICF until the last trial visit.

For definitions of AEs and SAEs, and procedures regarding reporting of SAEs refer to Section 7. Adverse events of special interest are defined in Section 7.2, and will be reported as AEs.

6.2.2.2 Clinical Laboratory Tests

Clinical laboratory parameters should be monitored at the time points specified in the [TRIAL SCHEDULES](#).

In addition to testing of all parameters (except coagulation and erythrocyte sedimentation rate [ESR]) at the central laboratory, platelet counts will also be assessed locally prior to IMP administration and muscle biopsy. Platelet counts as determined by the local laboratory need to be within normal laboratory references ranges before IMP administration (at the time points specified in the [TRIAL SCHEDULES](#)), or before performing a muscle biopsy. The samples for platelet count verification cannot be older than 3 days. Any discrepancy between the results of the local and central laboratory should be discussed with the medical monitor before any further IMP administration. The coagulation panel and ESR will only be tested locally; they will NOT be repeated at the central laboratory. If thrombocytopenia is reported during the trial after the first IMP administration, and if an immature platelet fraction (IPF) test is available at the local laboratory, IPF test results should be obtained in addition to the platelet count. The IPF is the ratio of immature platelets to the total number of platelets, indicating the percentage of young, so-called 'reticulated' platelets.

All clinical laboratory assays will be performed according to the local or central laboratory's normal procedures. Normal reference ranges which are age- and gender-specific (as applicable) are supplied by the respective laboratories and used to assess the clinical laboratory data for clinical significance and out-of-range pathological changes. The investigator should assess out-of-range clinical laboratory values for clinical significance, indicating if the value(s) is/are not clinically significant or clinically significant.

The following clinical laboratory assessments will be performed:

Biochemistry:

General	Liver function tests	Kidney function tests	Other
- sodium	- AST	- BUN	Cardiac Safety - creatine kinase myocardial band (CK-MB)
- potassium	- ALT	- creatinine	- cardiac troponin
- chloride	- ALP	- cystatin C	
- calcium	- GGT	- eGFR ^{a)}	
- magnesium	- bilirubin: direct, indirect, and total		
- phosphorus	- albumin		Muscle injury
- bicarbonate	- total protein		- creatine kinase
- glucose	- bile acids		
- CRP			
- IgG and IgM			
- LDH			

- a) Calculation of eGFR will be done by the central laboratory. The same method of calculation must be maintained for an individual subject.

Complement:

- C3	- C5a
- CBb	

Hematology:

- hemoglobin	- WBC differential ^{b)}
- hematocrit	- neutrophils
- red blood cell (RBC) count ^{a)}	- lymphocytes
- RBC parameters ^{a)} :	- monocytes
- mean corpuscular hemoglobin	- eosinophils
- mean corpuscular hemoglobin concentration	- basophils
- mean corpuscular volume	- platelet count ^{c)}
- white blood cell (WBC) count ^{b)}	- ESR

- a) RBC evaluation may include abnormalities in RBC count and/or RBC parameters and/or RBC morphology, which will then be reported by the laboratory.
- b) WBC evaluation may include any abnormal cells, which will then be reported by the laboratory. In addition, any other abnormal cells in a blood smear will also be reported
- c) If platelet clumping is observed in a local sample, the test should be repeated locally before IMP administration. In addition, a smear may be performed locally at the investigator's discretion.

Coagulation:

- PT ^{a)}	- INR
- aPTT	

- a) Depending on local laboratory's routine practice Coagulation panel test result may or may not include PT.

Urinalysis (dipstick):

- proteinuria	- hematuria
---------------	-------------

6.2.2.3 Physical Examination

A complete physical examination (including height, body weight and body systems) will be performed at screening. At all other time points, a symptom-directed physical examination will be performed. At baseline and after 24 weeks of MAD treatment (Week 25 visit), the symptom-directed physical examination will include a neurologic assessment. Physical examination results will be reported as normal/abnormal. Abnormal results will include underlying disease abnormalities. A neurologic assessment will be performed at Screening, Day 1 for each SAD and MAD cohort, Week 17 for each SAD cohort, and Week 25/EoT for each MAD cohort and at EoT and EoT follow-up for any subject in the MAD extension. Further details will be described in the site manuals (e.g. Laboratory Manual, Site Operations Manual, Pharmacy Manual).

Body weight will be measured at the indicated time points. A substantial change (as judged by the investigator) in body weight will be reported as an AE, and it will be discussed with the sponsor whether the dose calculation should be adjusted (see Section 5.2).

Treatment of any abnormality observed during this examination has to be performed according to local medical practice outside this trial or by referral to an appropriate health care provider. Abnormalities identified at screening (compared to a healthy person) will be documented in the subject's source documents and on the medical history eCRF. Worsening after screening will be captured as AEs on the AE eCRF page, when deemed clinically significant in the opinion of the investigator.

6.2.2.4 Vital Signs

Vital signs (i.e. pulse rate, systolic and diastolic blood pressure, respiratory rate, pulse oximetry, and body temperature) will be assessed in a standardized manner. Pulse rate and blood pressure will be measured after 5 minutes in supine position. Blood pressure should be determined by cuff (using the same method, the same arm, and in the same position throughout the trial). Any deviations from baseline vital signs, which are deemed clinically significant in the opinion of the investigator, will be recorded as an AE. The vital signs monitoring during the infusion should be done every 5 minutes for the first 15 minutes and every 15 minutes until the infusion is completed. If the infusion is stopped for any reason and restarted, vital signs are to be taken according to this schedule until the infusion is completed. Pulse oximetry will measure the oxygen saturation level using a small device attached to the subject's finger. The pulse oximetry device should remain in place throughout the IMP administration; any clinical findings during the continuous monitoring are to be reported. All vital signs will be noted as normal, abnormal not clinically significant, or abnormal clinically significant. Any abnormal clinically significant vital signs results are to be recorded as an AE.

6.2.2.5 Triplicate 12-Lead ECG and ECG Monitoring

Triplicate 12-lead ECGs will be recorded and interpreted locally at the specified time points. On Day 1 (SAD), a triplicate 12-lead ECG will be performed, within 30 minutes before the start of the IMP administration and within 15 minutes after the end of the infusion, and ECG monitoring will be performed during the infusion (accompanied by oximetry and vital signs monitoring). Additional ECG monitoring may be done during treatment if, in the opinion of the investigator, this is clinically indicated.

The subject will be instructed to rest in the supine position for 5 minutes before having an ECG assessment performed. If blood sampling or vital sign measurements are scheduled at the same

time point as the ECG recording, the procedures should preferably be initiated in the following order: ECG, vital signs and blood draw.

Any deviations from baseline values, which are deemed clinically significant in the opinion of the investigator, will be recorded as an AE.

6.2.2.6 Liver Ultrasound and Hepatic Elastography

A liver ultrasound including hepatic elastography to assess hepatic peliosis and other structural abnormalities will be performed during the screening period, at the baseline visit of SAD (if the screening liver ultrasound and/or hepatic elastography is older than 12 months), or before the baseline visit in the MAD part (if not performed during the screening period). The liver ultrasound and hepatic elastography results should be available before IMP administration.

Abnormalities identified at baseline will be documented in the subject's source documents and on the medical history eCRF page.

6.2.2.7 Pregnancy Test

A urine beta human chorionic gonadotropin (hCG) pregnancy test with a minimal sensitivity of 25 mL/IU will be performed on all female subjects of child-bearing potential at the specified time points, in case pregnancy is suspected, and/or upon withdrawal of the subject from the trial.

6.2.3 Pharmacokinetic Evaluations

Further details will be described in the site manuals (e.g. Laboratory Manual, Site Operations Manual, Pharmacy Manual).

6.2.3.1 Collection of Blood Samples for PK Evaluations

Blood samples for the determination of DYN101 levels in plasma will be collected by an indwelling catheter in the arm into vacuum tubes at the time points indicated in [Table 3](#). A sample should be taken immediately after the end of the infusion. The following post-dose samples should be taken relative to the end of the infusion.

Table 3: Pharmacokinetic Sampling Schedule

Time Point	Time Relative to Dosing on Day 1 (SAD/MAD)	Sampling Window
SAD and Washout		
Week 1, Day 1	Pre-dose (0h)	
	30 min after start of infusion (i.e. during infusion)	±10 min
	Immediately after the end of infusion	±10 min
	1h after the end of infusion	±10 min
	3h after the end of infusion	±10 min
	7h after the end of infusion	±1h
Week 1, Day 2	23h after the end of infusion	±3h
Week 1, Day 3	47h after the end of infusion	±3h
Week 2, Day 8	167h after the end of infusion	±1d
Week 3, Day 15	2 weeks post-dose	±3d
Week 5, Day 29	4 weeks post-dose	±3d
Week 9	8 weeks post-dose	±3d
Week 13	12 weeks post-dose	±3d
Week 17	16 weeks post-dose	±3d

Time Point	Time Relative to Dosing on Day 1 (SAD/MAD)	Sampling Window
MAD		
MAD Week 1, Day 1	Pre-dose (0h)	
	30 min post start of infusion (i.e. during infusion)	±10 min
	Immediately after the end of infusion	±10 min
	1h after the end of infusion	±10 min
	3h after the end of infusion	±10 min
	7h after the end of infusion	±1h
MAD Week 1, Day 2	23h after the end of infusion	±3h
MAD Week 1, Day 4	71h after the end of infusion	±3h
MAD Week 2	Week 1, Day 1* 167h after the end of infusion	±1d
MAD Week 12, Day 1	Pre-dose (0h)	
	30 min after start of infusion (i.e. during infusion)	±10 min
	Immediately after the end of infusion	±10 min
	1h after the end of infusion	±10 min
	3h after the end of infusion	±10 min
	7h after the end of infusion	±1h
MAD Week 12, Day 2	23h after the end of infusion	±3h
MAD Week 12, Day 4	71h after the end of infusion	±3h
MAD Week 13	Week 12, Day 1* (167h after the end of infusion)	±1d
MAD Week 25	Week 24* (167h after the end of infusion)	±1d

* Sample to be taken before the next infusion (if applicable).

6.2.3.2 Collection of Samples for Exploratory Pharmacokinetics

Collection of Blood Samples for Anti-Drug Antibodies

Blood samples for determination of ADA will be taken in the MAD part and the MAD extension part at the time points specified in the [TRIAL SCHEDULES](#).

Collection of Blood Samples for Metabolic Profiling

Blood samples for metabolic profiling of DYN101 will be taken in MAD Week 12 at 1 and 167 hours post-dose (see [Table 3](#)).

Collection of Urine for Metabolic Profiling

Urine for metabolic profiling will be collected in MAD Week 12 in the following manner:

- Subject should empty their bladder prior to, but as close as feasibly possible to, dose administration.
- Urine will be collected over a 24-hour interval. The window of collection will be based on the start of the infusion (e.g. if infusion start is recorded as 13:00, then the collection window will end the following day at 12:59).

Complete instructions on the collection of urine will be provided to the subject prior to the start of the collection. The subject may be confined to the clinic to collect this 24-hour urine sample.

Further details will be described in the site manuals (e.g. Laboratory Manual, Site Operations Manual).

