DNA sample (optional)	✓						
PROMIS and GAS questionnaires	✓						
EAT-10 Dysphagia questionnaire	✓						
Respiratory function ^{m)}	✓						
MyoGrip ^{m)}	✓						
MFM32 ^{m)}	✓						
Muscle ultrasound imaging ^{m)}	(✓) ⁿ⁾						
Muscle biopsy ^{m)}	✓ ^{o)}						
Single Dose Treatment							
Triplicate 12-lead ECG and ECG monitoring ^{p)}							
Start of IMP administration (IV) ^{q), r)}		✓					
PK Assessments							
Blood sample for PK ^{s)}	(✓) ^{t)}	✓	✓	✓	✓	✓	✓

AE: adverse event; BP: blood pressure; EAT-10: Eating Assessment Tool; ECG: electrocardiogram; EoT: End of Treatment; FU: follow-up; GAS: Goal Attainment Scaling; IMP: investigational medicinal product; IPF: immature platelet fraction; IV: intravenous; MFM: Motor Function Measure; PD: pharmacodynamics; PK: pharmacokinetics; PROMIS: Patient Reported Outcomes Measurement Information System; RR: respiratory rate; SAD: single ascending dose; SAE: serious adverse event.

- a) If needed, all assessments that need to be performed pre-dose can be done over 2 consecutive days (i.e. Day 0 or Day 1); any exceptions to doing over 2 consecutive days due to an open biopsy with general anesthetic must be discussed with the medical monitor in advance for approval. There must be at least 24 hours between an open biopsy with general anesthesia and IMP administration. The investigator is to get approval from the medical monitor if additional time is required to perform all needed Pre-dose/Baseline assessments.
- b) A symptom-directed physical examination (including a neurologic assessment) and measurement of body weight will be performed. A neurologic assessment is also to be performed.
- c) If baseline and IMP administration occur on the same day, vital signs should only be performed once, i.e. immediately before dosing.
- d) Vital signs are to be obtained prior to any PK samples.
- e) Vital signs are to be monitored continuously during infusion such that vital signs will be taken every 5 minutes for the first 15 minutes of the infusion and every 15 minutes until the infusion is completed. If the infusion is stopped for any reason and restarted, vital signs are to be taken according to this schedule until the infusion is completed. All vital signs will be noted as normal, abnormal not clinically significant, or abnormal clinically significant. Any abnormal clinically significant vital signs results are to be recorded as an AE.

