Time Window	±1d	±1d	±1d	±1d	±1d	±3d	±3d	±3d	±3d	±3d	±3d	±3d	±3d	±3d	±3d
Administrative															
Concomitant medications	✓	✓	✓	✓	✓	✓	✓	✓	✓	✓	✓	✓	✓	✓	✓
IMP administration (IV) ^{d)}	✓			✓		✓	✓	✓	✓	✓	✓	✓	✓	✓	✓
Safety Assessments															
Physical examination ^{e)}	✓									✓					
Triplicate 12-lead ECG	✓									✓					
Vital signs (pulse rate, BP, RR, temperature, pulse oximetry) ^{g)}	✓		✓	✓		✓	✓	✓	✓	✓	✓	✓	✓	✓	✓
Liver ultrasound including hepatic elastography	(✓) ^{g) h)}														
Platelet count ^{f) g) i)}	✓		✓ ^{k)}	✓		✓	✓	✓	✓	✓	✓	✓	✓	✓	✓
Clinical laboratory assessments ^{f) g) j)}	✓ ^{l)}	✓	✓	✓	✓	✓	✓	✓	✓	✓	✓	✓	✓	✓	✓
Cardiac troponin ^{f) g) k)}	✓					✓		✓				✓			
Complement assessments ^{f) g) k)}	✓					✓		✓				✓			
Coagulation assessments ^{f) g) m)}	✓		✓	✓		✓	✓	✓	✓	✓	✓	✓	✓	✓	✓
Erythrocyte sedimentation rate ^{f) g) m)}	✓		✓	✓		✓	✓	✓	✓	✓	✓	✓	✓	✓	✓
Urinalysis (dipstick) ^{g)}	✓					✓		✓				✓			
Urine pregnancy test ^{g) n)}	✓							✓				✓			
Collect AEs/SAEs	✓	✓	✓	✓	✓	✓	✓	✓	✓	✓	✓	✓	✓	✓	✓

MAD PART															
Trial Period	Multiple Dose Treatment Period ^{a) b)}														
Time Point: Day (D)/Week (W)	MAD W1			MAD W2		MAD W3	MAD W4	MAD W5	MAD W6	MAD W7	MAD W8	MAD W9	MAD W10	MAD W11	MAD W12
	D1 ^{c)}	D2	D4	D8	D11										
Time Window	±1d	±1d	±1d	±1d	±1d	±3d	±3d	±3d	±3d	±3d	±3d	±3d	±3d	±3d	±3d
PK Assessments															
Blood sample for PK	✓ ^{o)}	✓		✓											✓ ^{o)}
Blood sample for anti-drug antibodies	✓									✓					
Blood sample for metabolic profiling															✓ ^{p)}
24-hour urine collection for metabolic profiling															✓ ^{q)}
PD/Exploratory Efficacy Assessments															
Blood sample for biomarkers (optional) ^{g)}	✓									✓					
PROMIS and GAS questionnaires ^{g)}	✓									✓					
EAT-10 Dysphagia questionnaire ^{g)}	✓														
Respiratory function ^{g) r)}	✓			✓						✓					
MyoGrip ^{g) r)}	✓									✓					
MFM32 ^{g) r)}	✓									✓					

AE: adverse event; BP: blood pressure; EAT-10: Eating Assessment Tool; ECG: electrocardiogram; EoT: End of Treatment; FU: follow-up; GAS: Goal Attainment Scaling; IMP: investigational medicinal product; IPF: immature platelet fraction; IV: intravenous; MAD: multiple ascending dose; MFM: Motor Function Measure; PD: pharmacodynamics; PK: pharmacokinetics; PROMIS: Patient Reported Outcomes Measurement Information System; RR: respiratory rate; SAE: serious adverse event.

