- Where possible, the visits in the MAD part will take place on the same day of the week as Day 1 (and of the SAD part, if applicable). A window of ±3 days is allowed for visits as of Week 3, with a minimum of 4 days between 2 subsequent infusions. Assessments of a single visit can be split over 2 consecutive days, if required.
- Replacement subjects starting in the MAD part should sign an ICF for participation in the MAD part, and their eligibility will be assessed (see Trial Schedule for the Screening Period) before the first IMP administration in the MAD part (MAD Week 1 Day 1). If needed (to be discussed with the sponsor), these subjects will have a run-in period before they can start in the MAD part (see Trial Schedule for Run-in Period). A DNA sample (optional) and a muscle biopsy should be taken before the first IMP administration. If needed, replacement subjects in MAD1 and MAD2 may have the second muscle biopsy taken after 6 to 12 weeks of MAD treatment, after discussion with the sponsor.
- All assessments need to be done pre-dose.
- Slow infusion over 1 hour; subjects will be monitored on site by qualified site personnel for a minimum of 1 hour after the infusion for safety. Platelet counts as determined by the local laboratory need to be within normal ranges before IMP administration.

- e) A symptom-directed physical examination (and measurement of body weight at MAD Week 1 Day 1) will be performed.
- f) During an unscheduled visit which will occur between 6 weeks and 7 days prior to the baseline visit for subjects for whom the last visit in the SAD part will be more than 3 months before the baseline visit in the MAD part.
- g) To be performed pre-dose.
- h) Only applicable if a liver ultrasound and/or hepatic elastography was not performed during the screening period.

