3.3.3 Exploratory Endpoints

- Difference in mean change from baseline for clinical assessments in various affected clinical domains (respiratory, muscle strength and function, dysphagia) using the Pharmacokinetic Set by dose (cohort), for single or multiple administration, and by mutated gene (sub-cohort) at each post-baseline visit. The parameters to be analyzed for respiratory function are FVC (L), %FVC Predicted, FEV1 (L), %FEV1 Predicted, FEV1/FVC, MEP (cm H₂O), %MEP Predicted, MIP (cm H₂O), %MIP Predicted, Oxygen Saturation (%). The MyoGrip Test score will be used for analyzing muscle strength. The following parameters will be analyzed for muscle function; D1 Standing and transfers (%), D2 Axial and proximal motor function (%), D3 Distal motor function (%), Total MFM32 Score (%). Dysphagia will be assessed using the EAT-10 total score.
- Difference in mean change from baseline for PROMIS Questionnaire T-scores for the following domains (Anxiety, Depression, Fatigue, Pain Interference, Ability to Participate, and Physical Function) using the Pharmacokinetic Set by dose (cohort), for single or multiple administration, and by mutated gene (sub-cohort) at each post-baseline visit.
- Comparison of proportion of CGI-I responders (responders defined as responding 1 or 2) using the Pharmacokinetic Set by dose (cohort), for single or multiple administration, and by mutated gene (sub-cohort) at each post-baseline visit.
- Comparison of proportion of PGI-C responders (responders defined as responding 1 or 2) using the Pharmacokinetic Set by dose (cohort), for single or multiple administration, and by mutated gene (sub-cohort) at each post-baseline visit.
- Comparison of proportion of Goal Attainment Scaling (GAS) Questionnaire responders (responders defined as responding ‘YES – MUCH BETTER’, ‘YES – A LITTLE BETTER’) using the Pharmacokinetic Set by dose (cohort), for single or multiple administration, and by mutated gene (sub-cohort) at each post-baseline visit.
- Comparison of means of ADA against DYN101 using the Pharmacokinetic Set by dose (cohort), for single or multiple administration, and by mutated gene (sub-cohort) at each post-baseline visit.

- Comparisons of the metabolic profile of DYN101 in blood and urine using the Pharmacokinetic Set by dose (cohort), for single or multiple administration, and by mutated gene (sub-cohort) at each post-baseline visit.

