6.2.3.3 Analytical Methods

Plasma samples will be analyzed to determine concentrations of DYN101 using a validated, specific and sensitive method.

DYN101 metabolites in plasma and urine will be identified and profiled in an exploratory manner.

A validated ELISA method will be used to determine the presence and level of anti-DYN101 antibodies in plasma.

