6.2.7 Volume of Blood to be Drawn from Each Subject

All blood samples will be collected via an indwelling catheter. The volume of blood to be drawn from each subject is presented in Table 4.

Table 4: Volume of Blood to be Drawn from Each Subject

Assessment	Sample Volume (mL)	Number of Samples ^{a)}	Total Volume (mL)
Safety samples – clinical laboratory tests			
Biochemistry (8.5 mL)	8.5	16	136.0
Biochemistry (5.0 mL)	5.0	19	95.0
Bile Acids	3.5	35	122.5
Complement	5.0	1	5.0
Hematology	2.0	31	62.0
Coagulation - local	4.5	31	139.5
Platelet count – local	1.0	31	31.0
Cardiac troponin	2.5	14	35.0
Erythrocyte sedimentation rate - local	2.0	30	60.0
PK samples ^{b)}			
PK evaluations	4.0	33	132.0
Anti-drug antibodies	4.0	5	20.0
Metabolic profiling	4.0	2	8.0
Blood biomarkers samples (optional)	9.0	6	54.0
DNA sample (optional)	2.5	1	2.5
Total Volume of Blood (mL)	57.5		902.5

a) Not including any additional samples taken after MAD Week 25.

b) If a catheter is used, the first 1 mL is to be discarded and 3 mL is taken into an appropriate tube for PK samples. Therefore, a total of 4 mL is indicated as the sample volume.

Note: The above volume of blood to be taken for each assessment is an estimate. The volume of blood to be taken may vary according to the instructions provided by the manufacturer or laboratory for an individual assessment. The estimated total blood volume does not include blood draws during unscheduled visits. When more than 1 blood assessment is to be done at the same time point/period, if they require the same type of tube, the assessments may be combined.

The total blood volume to be collected is considered to be within the limits of standard blood donation.

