### 6.12.2 Anti-Drug Antibodies

The impact of immunogenicity (anti-drug antibodies, ADA) on the PK of DYN101 will be explored. Blood samples for determination of ADA will be taken in the MAD part and the MAD extension part at the time points specified in the Trial Schedules.

Descriptive statistics (n, mean, SD, median, min, max) of the observed values will be presented by treatment group (cohort, subcohort) and visit for each parameter.

All data will be listed.

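### For subjects entering through SAD, no anti-drug-antibody sample is planned before the first dose or during the SAD part, so the single-administration half of the ADA endpoint has no data from that part

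*Protocol*

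**What the plan says.** Protocol 6.2.3.2 states: "Blood samples for determination of ADA will be taken in the MAD part and the MAD extension part at the time points specified in the" (it then cites the visit tables). SAP 6.12.2 repeats this. In the Trial Schedules, the row "Blood sample for anti-drug antibodies" appears in the MAD part (Weeks 1 and 7), the MAD extension (Weeks 13, 19 and 25) and the follow-up after Week 25. It is absent from the screening, run-in, baseline/SAD and SAD follow-up tables. At SAD Day 1 the only row under PK assessments is "Blood sample for PK". The note to MAD Week 1 Day 1 says "All assessments need to be done pre-dose", so that first ADA sample precedes the first MAD dose but follows the SAD dose.

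Table 4 (Protocol 6.2.7) budgets "Anti-drug antibodies 4.0 5 20.0", that is 4.0 mL per sample, 5 samples, 20.0 mL.

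The exploratory endpoint in Protocol 3.3.3 is "Comparison of means of ADA against DYN101 using the Pharmacokinetic Set by dose (cohort), for single or multiple administration", by mutated gene and at each post-baseline visit. Protocol 6.2.3.4 says that ADA effects on the PK parameters will be assessed, and SAP 6.12.2 says "The impact of immunogenicity (anti-drug antibodies, ADA) on the PK of DYN101 will be explored". On the assay, Protocol 6.2.3.3 says "A validated ELISA method will be used to determine the presence and level of anti-DYN101 antibodies in plasma".

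**The concern.** All subjects except replacements pass through SAD before MAD. Their first ADA sample is thus taken after exposure, and the single-dose period has none. This has three consequences.

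- The endpoint asks for ADA after single administration, but the SAD part supplies no ADA data.
- The single-dose PK profiles, which are the first human PK data for this product, have no concurrent ADA value to set beside them.
- A subject already positive at MAD Week 1 may have had pre-existing reactivity or may have responded to the SAD dose. The plan gives no means of telling which. Because the MAD dose may differ from the SAD dose, such a positive also cannot safely be credited to the dose of the MAD cohort under which it would be tabulated.

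A response to the single dose that faded before MAD Week 1 would be missed altogether.

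**Working it through.** **1. Reproduce the plan's sample count.** Counting ADA ticks in the Trial Schedules up to MAD Week 25:

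| Period | ADA samples |
|---|---|
| Screening and run-in | 0 |
| Baseline and SAD Day 1 | 0 |
| SAD follow-up and washout | 0 |
| MAD part (Weeks 1, 7) | 2 |
| MAD extension (Weeks 13, 19, 25) | 3 |
| Total | 5 |

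5 × 4.0 mL = 20.0 mL, as in Table 4. The count leaves no room for an unlisted SAD sample.

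**2. Check that the counting method is sound.** The same count on other rows also matches Table 4.
- PK samples: 14 (SAD and washout) + 9 (MAD Week 1) + 9 (MAD Week 12) + 1 (MAD Week 25) = 33.
- Optional biomarker samples: 1 (SAD baseline) + 2 + 3 = 6. This row does have a SAD baseline draw; ADA does not.
- Total: 136.0 + 95.0 + 122.5 + 5.0 + 62.0 + 139.5 + 31.0 + 35.0 + 60.0 + 132.0 + 20.0 + 8.0 + 54.0 + 2.5 = 902.5 mL.

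**3. Interval from first exposure to first ADA sample.** Protocol 3.1.1 gives 4 weeks of SAD follow-up plus a washout of at least 12 weeks: 4 + 12 = 16 weeks. The schedule agrees, since SAD Week 17 is Day 113 and (113 − 1)/7 = 16.0 weeks. If the 3-day early window of that visit carried over to the MAD start, the nominal minimum would be (113 − 3 − 1)/7 = 15.6 weeks. Subjects waiting for their MAD cohort to open would have a longer gap.

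**4. What each type of subject can show.**

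| Subject | Drug-naive ADA samples | Can origin be classed? |
|---|---|---|
| SAD entry, positive at MAD Week 1 | 0 of 5 | No |
| SAD entry, negative at MAD Week 1, positive later | 0 of 5 | Yes, converted during MAD |
| SAD entry, transient response in washout | 0 of 5 | Not detected |
| Replacement entering at MAD | 1 of 5 (MAD Week 1 pre-dose) | Yes |

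All SAD-entry subjects (about 18 planned) lack a drug-naive value. The number who would be ambiguous is the number positive at MAD Week 1, and the documents give no figure from which to estimate it.

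**5. After the fix.** Two more samples: 5 + 2 = 7; 7 × 4.0 = 28.0 mL; 902.5 + 8.0 = 910.5 mL, an increase of 8.0/902.5 = 0.9%.

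**The case against.** The other side has several good points.

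- **Origin is not a stated objective.** Protocol 2.3 asks only about the presence of ADA, and no section promises to separate pre-existing from induced antibodies. This stands. It does not answer the endpoint's reference to single administration.
- **MAD Week 1 pre-dose is itself a reading after a single dose.** True, and it is the only one scheduled. It comes about 16 weeks or more after that dose, exists only for subjects who proceed to MAD, and lies outside the SAD part. A subject who discontinues after SAD is encouraged to have the Week 25 assessments, which include ADA. That sample could come sooner but is still post-exposure.
- **No planned ADA statistic needs a baseline.** A reader might infer that SAP 6.2.3, which fixes baseline before the first SAD dose, makes the ADA analysis impossible. It does not: SAP 6.12.2 summarises observed values only, with no change from baseline.
- **The ADA–PK exploration survives for multiple dosing.** A reader might infer that it fails altogether. ADA is measured pre-dose at MAD Week 1, when the first MAD profile starts, and at Week 13, when the Week 12 profile ends. Relating ADA status to MAD PK needs a measurement near the profile, not knowledge of origin. Only single-dose PK lacks one.
- **Termination.** SAP sections 8 and 10 limit reporting to the IDMC outputs and selected efficacy parameters. ADA listing 16.2.8.11 is struck through, and ADA table 14.4.3.1 is not marked for any IDMC meeting. This greatly reduces the practical effect. SAP 3.3 and 6.12.2 still carry the ADA comparison, so the mismatch remains in the plan as written.

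**Conclusion.** The gap is real but narrow. For SAD-entry subjects, 0 of 5 scheduled ADA samples up to MAD Week 25 are drug-naive and 0 fall in the SAD part; the first comes about 16 weeks or more after first exposure in those who proceed to MAD. The single-administration part of the endpoint therefore has no ADA data from the SAD part, single-dose PK has no concurrent ADA value, and origin is undetermined for anyone positive at MAD Week 1.

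The stronger reading, that pre-existing and induced antibodies cannot be separated in this trial at all, is not supported: later converters and replacement subjects can be classed. The conclusion rests on the Trial Schedules being complete for ADA, which the Table 4 count confirms. Severity is low, because ADA is exploratory, no primary or secondary endpoint depends on it, and the abbreviated report omits the ADA listing.

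**What to change.** **In the plan.** Add an ADA sample at the existing SAD Day 1 pre-dose draw and another at an existing washout draw (Day 29 or Week 17; both already have a PK sample). Update the SAD schedules, Protocol 6.2.3.2 and Table 4 (ADA from 5 to 7 samples, 20.0 to 28.0 mL; total 902.5 to 910.5 mL). In SAP 6.12.2, class each subject as ADA-negative, pre-existing or treatment-induced against the Day 1 sample.

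**For subjects already dosed.** Assay leftover Day 1 pre-dose plasma only where volume, stability and consent allow. The assay uses plasma and Protocol 6.2.8 permits exploratory use of leftovers, but the route is conditional. Table 4 note b shows 3 mL kept per PK draw when a catheter is used, with no stated spare. Section 10.4.4 makes storage optional, has samples destroyed where consent is not given, restricts use to understanding CNM, and sends analyses not pre-defined in the protocol to a separate report. Where no such assay is possible, label any reported MAD Week 1 positive in a SAD-entry subject 'post-exposure, origin undetermined' and limit the ADA endpoint wording to multiple administration.

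**Cost.** Two more assay runs per subject, at most 8 mL more blood, and edits to the schedule, Table 4 and SAP. No new visit or procedure is needed. With the trial terminated, the labelling and endpoint wording are the parts that can still be applied without new samples.
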